**2.2 Secondary**

- 2.21 To determine the  $\geq$  very good partial response (VGPR) and complete response (CR) rate of pembrolizumab added to standard doses of ixazomib and dexamethasone in relapsed myeloma.
- 2.22 To determine the progression free survival and overall survival among patients with relapsed MM following treatment with the combination of pembrolizumab, ixazomib and dexamethasone.
- 2.23 To determine the toxicities associated with pembrolizumab added to standard doses of ixazomib and dexamethasone in patients with relapsed MM.

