## 10.6 Required Routine Reporting

### 10.61 Baseline and Adverse Events Evaluations

Pretreatment symptoms/conditions to be graded at baseline and adverse events to be graded at each evaluation.

Grading is per CTCAE v4.0 **unless** alternate grading is indicated in the table below:

CTCAE SYSTEM/ORGAN/CLASS	Adverse event/Symptoms	Baseline	Each evaluation
Blood and lymphatic system disorders	Febrile neutropenia	X	X
Gastrointestinal Disorders	Baseline # of stools	X	
	Constipation		X
	Diarrhea		X
	Nausea	X	X
	Vomiting	X	X
General disorders and administration site conditions	Fatigue	X	X
Infections and infestations	Sepsis	X	X
Investigations	Creatinine increased	X	X
	Neutrophil count decreased	X	X
	Platelet count decreased	X	X
Skin and subcutaneous tissue disorders	Rash, maculo-papular	X	X

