### 10.62 Submit via appropriate MCCC Case Report Forms (i.e., paper or electronic, as applicable) the following AEs experienced by a patient and not specified in Section 10.6:

10.621 Grade 2 AEs deemed *possibly, probably, or definitely* related to the study treatment or procedure.

10.622 Grade 3 and 4 AEs regardless of attribution to the study treatment or procedure.

10.623 Grade 5 AEs (Deaths)

10.6231 Any death within 30 days of the patient's last study treatment or procedure regardless of attribution to the study treatment or procedure.

10.6232 Any death more than 30 days after the patient's last study treatment or procedure that is felt to be at least possibly treatment related must also be submitted as a Grade 5 AE, with a CTCAE type and attribution assigned.

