## 10.8 Additional Event Reporting Instructions

### 10.81 Merck

All adverse events will be recorded from the time the consent form is signed through 30 days following cessation of treatment and at each examination on the Adverse Event case report forms/worksheets. The reporting timeframe for adverse events meeting any serious criteria is described above.

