#### 16.32 Secondary Outcome Analyses

16.321 The  $\geq$ VGPR response rate with pembrolizumab added to Ixazomib and dexamethasone will be estimated by the number of patients who achieve a VGPR, CR, or sCR at any time divided by the total number of evaluable patients. Exact binomial 95% confidence intervals for the true success rate will be calculated.

16.322 The complete response rate with pembrolizumab added to Ixazomib and dexamethasone will be estimated by the number of patients who achieve a CR or sCR at any time divided by the total number of evaluable patients. Exact binomial 95% confidence intervals for the true success rate will be calculated.

16.323 Survival time is defined as the time from date of first treatment to death due to any cause. The distribution of survival time will be estimated using the method of Kaplan-Meier.

16.324 Progression-free survival is defined as the time from date of first treatment to the earliest date of documentation of disease progression or death due to any cause. Patients who receive subsequent treatment for myeloma before disease progression will be censored on the date of their last disease assessment prior to initiation of the subsequent treatment. Transplant will not be considered subsequent treatment. The distribution of progression-free survival will be estimated using the method of Kaplan-Meier

16.325 Adverse Events: All eligible patients that have initiated treatment will be considered evaluable for assessing adverse event rate(s). The maximum grade for each type of adverse event will be recorded for each patient, and frequency tables will be reviewed to determine patterns. Additionally, the relationship of the adverse event(s) to the study treatment will be taken into consideration.

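### Section 16.325 tabulates each patient's maximum adverse event grade without using the baseline grade or an onset date; applied literally, stable entry abnormalities would inflate low-grade toxicity rates

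*Combined protocol and SAP*

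**What the plan says.** Secondary goal 2.23 is "To determine the toxicities associated with pembrolizumab added to standard doses of ixazomib and dexamethasone in patients with relapsed MM". Section 16.325 is the analysis for it. The population is eligible patients who have started treatment, which selects patients and not events. The tabulation rule is "The maximum grade for each type of adverse event will be recorded for each patient, and frequency tables will be reviewed to determine patterns". The section closes with "Additionally, the relationship of the adverse event(s) to the study treatment will be taken into consideration", and does not say how.

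Three collection rules feed that table:

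- Section 10.61: "Pretreatment symptoms/conditions to be graded at baseline and adverse events to be graded at each evaluation". Nine terms are marked for both baseline and each evaluation: febrile neutropenia, nausea, vomiting, fatigue, sepsis, creatinine, neutrophils, platelets and maculo-papular rash.
- Section 10.62, for events that Section 10.6 does not specify: "Grade 2 AEs deemed *possibly, probably, or definitely* related to the study treatment or procedure", and "Grade 3 and 4 AEs regardless of attribution to the study treatment or procedure".
- Section 10.81 (the instructions for one drug supplier): "All adverse events will be recorded from the time the consent form is signed through 30 days following cessation of treatment".

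Section 3.13 admits patients with an ANC down to 1000/mm3, platelets down to 75,000/mm3 and creatinine clearance down to 30 mL/min.

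**The concern.** The plan collects a baseline grade for these nine terms and then gives it no role in the analysis. A maximum taken over all gradings cannot separate a patient whose count fell on treatment from one whose count was low on arrival and stayed there. Entry abnormality is foreseeable in these terms, because the eligibility floors allow it and Section 3.14 requires prior proteasome inhibitor, IMiD and anti-CD38 therapy.

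At stake are the descriptive toxicity rates. With no control arm, nothing in the trial shows how much of a reported low-grade rate was already there. With about 37 patients, a handful of such cases visibly changes a percentage. The silence also lets two analysts produce different tables from the same data.

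**Working it through.** **1. Is there a plan figure to reproduce?** No: the documents state no adverse event rate. The design figures in Section 16.22 reproduce to rounding (significance level 0.0954 against .095; power 0.8526 against 0.853) and use no adverse event input. This point therefore leaves the primary endpoint and error rates untouched.

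**2. Does any section supply the missing rule?** Sections 10.61, 10.62, 10.81, 16.4 and 16.52 were read against 16.325. None defines a treatment-emergent event, a baseline comparison or an event window for the adverse event summary. Baseline and start date are used elsewhere: survival and progression-free survival run from first treatment (16.323, 16.324), and new-cycle criteria refer to baseline severity (8.11).

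**3. Literal application to one patient.** ANC is 1,200/mm3 at screening and at every visit. Section 8.3 treats counts above 1.0 x 10^9/L up to the lower limit of normal as a decreased neutrophil count. If the laboratory's lower limit exceeds 1.2 x 10^9/L (an assumption), this patient carries a nonzero grade at each evaluation. The maximum is that grade, so the patient is tabulated. The change from baseline is none. Unchanged fatigue behaves the same way.

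**4. Illustration of size.** Both inputs are assumptions:

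- b = share of patients with a stable abnormality at baseline, always re-recorded on study and never discounted;
- t = share who develop the event or worsen, independent of b.

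Tabulated any-grade rate = b + (1 - b)t. Excess over t = b(1 - t). Patient counts use the 37 of the design as denominator; the adverse event population could differ slightly.

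| b | t | Tabulated rate | Patients of 37 | New or worsened, of 37 | Excess |
|---|---|---|---|---|---|
| 10% | 20% | 28% | 10.4 | 7.4 | 3.0 |
| 20% | 20% | 36% | 13.3 | 7.4 | 5.9 |
| 30% | 20% | 44% | 16.3 | 7.4 | 8.9 |
| 40% | 20% | 52% | 19.2 | 7.4 | 11.8 |

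Varying t from 10% to 40% as well, the excess runs from 37 x 0.10 x 0.60 = 2.2 to 37 x 0.40 x 0.90 = 13.3 patients per term. If only half of the stable abnormalities were re-recorded, the excess halves: for b = 40% and t = 20%, the rate is 0.20 + 0.5 x 0.40 x 0.80 = 36%.

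**5. Higher grades.** Section 3.13 limits severity at entry for the laboratory terms. A patient who goes from Grade 1 to Grade 3 is shown as Grade 3 under either method. The distortion therefore sits mainly in the low grades.

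**The case against.** The best defense is that the plan is silent, not wrong. Section 10.61 names pretreatment conditions separately from adverse events and records a baseline stool count beside on-treatment diarrhea, which suggests that baseline is meant as a reference. Investigators can rate a stable abnormality as unlikely or unrelated (10.3), and 16.325 says that relationship will be considered. Section 10.62 already removes unrelated Grade 2 events.

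Part of this stands. A reader might infer that the plan declares stable abnormalities to be toxicities of the regimen; it does not. The attribution step could remove some of them in practice.

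It does not close the gap. No rule says how attribution or baseline enters the table. The 10.62 filter covers only events outside the 10.61 list, so it does not reach the terms at issue, and it passes Grade 3 and 4 events whatever their attribution. Attribution is also a different filter from change: Section 15.17 lists neutropenia and thrombocytopenia as very common with ixazomib, so an unchanged low count could be rated possible, while a new event judged unrelated would be dropped.

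On pre-dose events the defense is stronger. The consent start date is a supplier recording clause, Section 10.0 defines an adverse event by use of a drug, and treatment must begin within 14 days of registration (6.17). Such events could enter, but this is minor.

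**Conclusion.** The gap is real and limited. Section 16.325 sets an operative rule without baseline or onset reference, and under that rule stable entry abnormalities in the terms graded at baseline would overstate low-grade rates in the tables for goal 2.23. The change is worth making because the baseline data needed are already collected.

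The size cannot be established from the documents. The 28% to 52% range, against 20%, rests wholly on the assumed b and t and on every stable abnormality being re-recorded; it is not an estimate for this trial.

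Three stronger readings are not supported:

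- That the safety rules are compromised. The DLT definition (16.4) and the stopping rule (16.52) both require at least possible attribution, and the stopping rule counts only Grade 4 or higher non-hematologic events. They are largely, though not perfectly, protected.
- That a toxicity comparison with ixazomib plus dexamethasone would be biased. None is planned; Section 16.21 cites only a response rate for that doublet.
- That Grade 3 or higher rates are inflated to the same degree. Entry limits make that unlikely.

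**What to change.** In Section 16.325, define the events to be tabulated as those that start, or worsen in grade over the 10.61 baseline, on or after the first dose and up to a stated end date. The 30 days after cessation of treatment, already used for recording in 10.81, is one choice. Tabulate the maximum such grade per patient and term twice: regardless of attribution, and for events at least possibly related. Keep the unadjusted maximum-grade table as supportive.

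State also what happens where Section 10.61 calls for no baseline grade, as with constipation, diarrhea (only a stool count) and unlisted terms. There only the onset-date part can be applied directly.

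The cost is a short addition to the text, one programming step and additional tables. No new data are needed for the terms graded at baseline, and the sample size and decision rules do not change.

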### 16.33 Correlative Analyses

16.331 PDL-1 expression on myeloma cells and non-tumor cell compartments from the bone marrow will be assessed at baseline. Each measure will be summarized descriptively by median, min, max and interquartile range.

16.332 Markers of T-cell activation and exhaustion will be summarized descriptively by median, min, max, and interquartile range at each time point. Patterns over time will be summarized by absolute difference or relative change. Changes across time will be assessed using paired analyses, including Wilcoxon signed rank tests. Jitplots will be used to visually examine differences between groups for continuous factors.

16.333 NK cell function and numbers will be summarized descriptively by median, min, max, and interquartile range at each time point. Patterns over time will be summarized by absolute difference or relative change. Changes across time will be assessed using paired analyses, including Wilcoxon signed rank tests. Jitplots will be used to visually examine differences between groups for continuous factors.

16.34 Over Accrual: If more than the target number of patients are accrued, the additional patients will not be used to evaluate the stopping rule or used in any decision making processes; however, they will be included in final endpoint estimates and confidence intervals.

### 16.4 Early Safety Analysis

An early safety analysis will be performed after the first 6 patients have been accrued to the study and observed for at least 42 days. Accrual will be temporarily halted while these patients are evaluated. If 2 or more of the first 6 patients experience a DLT as defined below, then accrual to the study will continue to be temporarily halted while the study team determines if changes to the dosing schedule are warranted.

Toxicity will be measured per NCI-CTCAE version 4. DLT is defined as an adverse event occurring during the first cycle of treatment that is possibly, probably, or definitely related to study treatment and that meets one of the following:

- Any  $\geq$ Grade 4 neutrophil count decrease or platelet count decrease that persists  $>7$  days
- Any  $\geq$ Ggrade 3 infections
- $\geq$ Grade 3 erythema multiforme, ulceration, or urticarial that does not resolve to  $\leq$ Grade 2 within 3 weeks
- $\geq$ Grade 3 bronchial obstruction, pneumonitis, or wheezing
- $\geq$ Grade 3 allergic reaction or autoimmunity
- All other  $\geq$ Grade 3 non-hematologic toxicities (with the exception of electrolyte abnormalities that are reversible and asymptomatic) that does not resolve to  $\leq$ Grade 2 in  $\leq$ 72 hours despite optimal supportive medications

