**Schema**

If a patient is deemed ineligible or a cancel, please refer to Section 13 for follow-up information.

Cycle length = 84 days

Patients are allowed to collect stem cells after 1 cycle of initial therapy. Stem cells can be collected using standard institutional protocols. Any delay beyond 4 weeks should be discussed with the study PI prior to reinitiating protocol therapy.

Generic name: Ixazomib Brand name(s): Ninlaro® Mayo Abbreviation: MLN9708 Availability: Provided by Takeda	Generic name: Dexamethasone Brand name(s): Decadron® Mayo Abbreviation: DXM Availability: Commercial	Generic name: Pembrolizumab Brand name(s): Keytruda® Mayo Abbreviation: MK-3475 Availability: Provided by Merck
---	---	--

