## 7.0 Protocol Treatment

### 7.1 Treatment Schedule

Cycle length: 84 days.

Agent	Route	Dose	Day	Retreatment
Ixazomib	PO	4 mg	1, 8, 15, 29, 36, 43, 57, 64, 71	Every 84 days
Pembrolizumab	IV	200mg	Day 1, 22, 43, 64	Every 84 days
Dexamethasone	PO	40 mg	1, 8, 15, 29, 36, 43 57, 64, 71	Every 84 days

7.2 For this protocol, the patient must return to the consenting institution (Mayo Clinic) for evaluation at least every 21 days ( $\pm$  1 day). Treatment by a local medical doctor (LMD) is not allowed. Note: If patient is stable after 2 cycles, physical exam can be reduced to Weeks 1 and 7 of each cycle.

7.3 Patients are allowed to collect stem cells after 1 cycle of initial therapy. Stem cells can be collected using standard institutional protocols. Any delay beyond 4 weeks should be discussed with the study PI prior to reinitiating protocol therapy.

7.4 Patients should be instructed to swallow ixazomib capsules whole, with water, and not to break, chew, or open the capsules. The ixazomib should be taken on an empty stomach (no food or drink apart from 240 mL of water), at least 1 hour before or no sooner than 2 hours after food. Each capsule should be swallowed separately with a sip of water. A total of approximately 240 mL (about 1 cup/8 oz) of water should be taken with the capsules.

Missed doses can be taken as soon as the patient remembers as long as the next scheduled dose is 72 hours or more away. Patients who vomit a dose after ingestion will not receive an additional dose, but should resume dosing at the time of the next scheduled dose.

Drug will be administered only to eligible patients under the supervision of the investigator or identified sub-investigator(s). The drug will be prepared under the supervision of a pharmacist, or appropriately qualified and trained personnel.

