## 16.0 Statistical Considerations and Methodology

### 16.1 Overview

This is a phase II study of a novel regimen of Pembrolizumab with ixazomib and dexamethasone for treatment of relapsed multiple myeloma patients requiring therapy. This study is designed to assess the overall response rate associated with therapy with pembrolizumab added to standard doses of ixazomib and dexamethasone in patients with relapsed multiple myeloma using a single stage phase II study design with an interim analysis.

16.11 Endpoint: The primary endpoint of the trial is the overall response rate. A success will be defined as a PR or better noted as the objective status on two consecutive evaluations. Response will be evaluated using all cycles. Throughout Section 16.0, response will be considered synonymous with “success”, unless specified otherwise.

16.12 Sample Size: The single-stage study design with an interim analysis to be used is fully described below. A minimum of 14 and a maximum of 37 evaluable patients will be accrued in the phase II study unless undue toxicity is encountered. We anticipate accruing an additional 4 patients to account for ineligibility, cancellation, major treatment violation, or other reasons for a maximum of 41 patients. All patients meeting the eligibility criteria who have signed consent and received at least one dose of treatment will be considered evaluable for response, with the exception of patients who are determined to be a major violation.

16.13 Accrual Rate and Study Duration: The anticipated accrual rate is 2-3 evaluable multiple myeloma patients per month. At this rate, it will likely take about 1.5 years to enroll the patients. The maximum total study duration is expected to be approximately 4.5 years, or until the last patient accrued has been observed for at least 3 years. The earliest date anticipated for presentation of results is at approximately 2 years, or when the last patient accrued has been observed for at least 6 months.

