#### 16.52 Adverse Event Stopping Rules

The stopping rules specified below are based on the knowledge available at study development. We note that the Adverse Event Stopping Rule may be adjusted in the event of either (1) the study re-opening to accrual or (2) at any time during the conduct of the trial and in consideration of newly acquired information regarding the adverse event profile of the treatment(s) under investigation. The study team may choose to suspend accrual because of unexpected adverse event profiles that have not crossed the specified rule below.

Accrual will be temporarily suspended to this study if at any time we observe events considered at least possibly related to study treatment (i.e. an adverse event with attribute specified as “possible,” “probable,” or “definite”) that satisfy one of the following:

- if 2 or more patients in the first 6 treated patients experience a grade 4 or higher non-hematologic adverse event at least possibly related to treatment.
- if after the first 6 patients have been treated, 40% of all patients experience a grade 4 or higher non-hematologic adverse event at least possibly related to treatment.

We note that we will review Grade 4 and 5 adverse events deemed “unrelated” or “unlikely to be related”, to verify their attribution and to monitor the emergence of a previously unrecognized treatment-related adverse event.

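### The early safety look may be taken at day 42, but DLTs count over an 84-day first cycle, and no numeric DLT rule covers those that come after the look

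*Combined protocol and SAP*

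**What the plan says.** - **Timing of the look.** Section 16.4 sets an early safety analysis "performed after the first 6 patients have been accrued to the study and observed for at least 42 days". Accrual is halted while these patients are evaluated.
- **What counts.** In the same section, "DLT is defined as an adverse event occurring during the first cycle of treatment", with at least possible relation to study treatment and one of a list of criteria. Most of the criteria start at grade 3. One is a grade 4 neutrophil or platelet decrease lasting more than 7 days.
- **Consequence.** If 2 or more of the six have a DLT, "accrual to the study will continue to be temporarily halted while the study team determines" whether the dosing schedule should change.
- **Cycle length.** The Schema gives "Cycle length = 84 days" and section 7.1 gives "Cycle length: 84 days".
- **Accrual.** Section 16.13: "The anticipated accrual rate is 2-3 evaluable multiple myeloma patients per month".
- **Continuing rule.** Section 16.52: "Accrual will be temporarily suspended to this study if at any time we observe events considered at least possibly related to study treatment" that meet one of two criteria. The first applies "if 2 or more patients in the first 6 treated patients experience a grade 4 or higher non-hematologic adverse event"; the second applies after the first six, at 40% of all patients. Both count only grade 4 or higher non-hematologic events.

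**The concern.** The guaranteed observation is half the window over which a DLT is counted. Both statements can be followed together, but the result is that accrual may re-open while some of the first six can still have a DLT that belongs in the count. Section 16.4 does not say what happens to such a DLT. The continuing rule in 16.52 uses a narrower event definition and does not replace the DLT rule. At stake is whether the sponsor's own 2-of-6 threshold is applied to the sponsor's own DLT window in the first patients given this combination.

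**Working it through.** **1. No stated figure to reproduce.** The documents give no operating characteristics for the 2-of-6 rule. The only stated probabilities belong to the response design in 16.22. They reproduce from the exact two-stage binomial (significance level 0.0954 against 0.095; power 0.8526 against 0.853), and this point does not touch them.

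**2. Is the rule read once?** Section 16.4 plans one analysis. Continuing a halt makes sense only while the halt for that analysis is in force. Where the plan wants a rule to keep running it says so, as in 16.52.

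**3. Treatment scheduled by day 42 (section 7.1).** Pembrolizumab on days 1 and 22: 2 of 4 doses. Ixazomib on days 1, 8, 15, 29 and 36: 5 of 9 doses.

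**4. Which DLTs escape both rules.** Grade 3 DLTs and persistent grade 4 neutrophil or platelet decreases are outside 16.52. Suppose one of the six has a grade 3 DLT before the look and another has a grade 4 non-hematologic DLT after it. That is 2 of 6 by the 16.4 definition. The look saw 1, and 16.52 counts 1 (1/6 = 17%, below 40%). Neither rule is met.

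**5. Follow-up at the look.** Assume even accrual, the 42 days running from first dose, and a lag L from the sixth patient's day 42 to the reading. The patient enrolled k places before the sixth has

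follow-up = min(84, 42 + L + k × 30.44 / monthly rate), k = 0 to 5.

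With L = 0:
- 2 per month: 42, 57.2, 72.4, 84, 84, 84 days. The sum is 423.7 of 6 × 84 = 504 patient-days (84%), with 3 patients still inside the window.
- 3 per month: 42, 52.1, 62.3, 72.4, 82.6, 84 days. The sum is 395.5 of 504 (78%), with 5 still inside, one of them at day 82.6.

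**6. Chance that the threshold is reached only after the look.** Let q be the true first-cycle DLT rate (assumed; the documents give none). With constant hazard, the chance of a DLT by day t is 1 − (1 − q)^(t/84). P(at least 2 of 6) comes from the Poisson-binomial over the six follow-up times. Subtracting it from the full-window value 1 − (1 − q)^6 − 6q(1 − q)^5 gives the table, in percentage points (2 per month, 3 per month):

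| q | Full-window P(≥2 of 6) | L = 0 | L = 14 days | L = 28 days | L = 42 days |
|---|---|---|---|---|---|
| 10% | 0.114 | 2.9, 3.9 | 1.5, 2.0 | 0.5, 0.7 | 0 |
| 20% | 0.345 | 7.3, 9.8 | 3.7, 4.8 | 1.2, 1.6 | 0 |
| 25% | 0.466 | 8.8, 11.9 | 4.3, 5.7 | 1.5, 1.9 | 0 |
| 33% | 0.642 | 9.7, 13.4 | 4.7, 6.2 | 1.5, 2.0 | 0 |
| 40% | 0.767 | 9.1, 12.8 | 4.3, 5.7 | 1.4, 1.8 | 0 |
| Window seen | | 84%, 78% | 92%, 89% | 97%, 96% | 100% |
| Patients still inside | | 3, 5 | 2, 3 | 1, 2 | 0 |

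**7. Sensitivity.** At q = 33% and L = 14 days, halving the hazard in days 43-84 relative to days 1-42 gives 3.0 and 4.0 points; doubling it gives 6.4 and 8.5. Section 16.4 does not say when the 42 days start, and section 6.17 allows treatment to begin up to 14 days after registration. If the clock ran from registration with a full 14-day delay, the share of the window seen with no lag would fall to 74% (2 per month) or 64% (3 per month).

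**The case against.** The strongest reply is that 42 days is a minimum, the halt has no stated end, and the 2-of-6 sentence has no cut-off date. A study team could hold accrual until all six finish cycle 1 and comply fully; the gap is then zero. That stands, but the plan permits the longer hold without requiring it.

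A second reply is that late events would not go unnoticed:
- The study team may suspend accrual for unexpected profiles and may adjust the stopping rule at any time (16.52).
- The study may be discontinued for safety concerns (13.6), adverse events weigh in any decision to terminate (16.23), and accrual may be suspended if it is extremely rapid (16.214).
- Review takes place at least twice a year (16.51).
- Serious events reach the sponsor quickly (10.41, 10.81), and grade 3-4 events are reported whatever their attribution (10.62).
- Section 8 gives dose modification rules for the individual patient, and blood counts are weekly in cycle 1 (4.1).

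All of this is correct and lowers the stakes, but none of it is a numeric DLT rule. Expedited reporting also has a gap here: section 10.32 exempts neutrophil and platelet decreases up to grade 4 without hospitalization, although such a decrease is a DLT if it persists at grade 4 beyond 7 days. Those events still come in by routine reporting, and a clinically important rise in the rate of serious suspected reactions must be expedited.

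Third, the percentages rest on an assumed DLT rate, onset pattern, accrual pattern and lag, and run from zero to about 13 points with the clock at first dose. That is fair. They show scale and are not estimates.

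**Conclusion.** The concern holds as a cheap improvement. The mismatch between at least 42 days of observation and an 84-day DLT window is certain from the text. The single reading is the natural one, though it is not stated in so many words. Followed as written, the plan can re-open accrual on an incomplete DLT count for the first six, with no stated way to count a second DLT later in cycle 1.

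The size depends mostly on the lag before the look is read. With the clock at first dose, constant hazard and even accrual at 2-3 per month, the chance of reaching 2 of 6 only after the look is 3-4 points at a 10% DLT rate and 9-13 at 25-40% with no lag. With a 14-day lag it is 1.5-2 and 4-6 points.

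The consequence is limited. Reaching the threshold prolongs a temporary halt for study-team review; it does not end the trial. The response-rate decision rule, significance level and power are unaffected.

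**What to change.** Reconcile the observation period and the DLT window in 16.4. The smallest change keeps the day-42 look and adds three statements:

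1. The 42 days run from first dose.
2. DLTs in the first six patients continue to be counted through the end of cycle 1 (day 84).
3. If the cumulative number of these patients with a DLT reaches 2 after accrual has re-opened, accrual is halted again for the same study-team review.

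The sponsor could instead hold the look until all six have completed cycle 1, at the price of a longer first halt. Neither option sets a dose or treatment rule.

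The cost of the smallest change is one or two sentences, with no extra patients, visits or procedures. The downside is a possible second accrual pause, whose length the plan does not fix. Its chance is the figure in the table above, for example 5-6 points at an assumed 33% DLT rate with a 14-day lag, and it would occur only when the plan's own threshold is met.
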